6.6.9.1.1. Statistical Methods for All-cause Hospitalization Analysis

The exact method described in section 6.6.1 accounting for the follow-up time post-dosing/randomization is to be performed for estimating the relative risk reduction (i.e., efficacy) in all-cause hospitalizations associated with nirsevimab compared to no intervention, overall and in each country at the different timepoints considered above.

If a participant experiences multiple hospitalizations, only the first episode is considered for the endpoint in the main analysis.

The Poisson regression model described in section 6.6.2.1 is considered as a sensitivity analysis for the post-hoc analysis, with a modification compared to the study protocol: all hospitalizations are counted, not just the first episode. A negative binomial model may be used if better fitted with the data, particularly in case of overdispersion.

This is a post-hoc analysis performed to assess the risk reduction in all-cause hospitalizations associated with nirsevimab and its results should be presented as such. No statistical conclusion should be derived from this post-hoc analysis on its own, particularly no p-values should be presented.

6.6.9.2. Incidence of RSV LRTI Hospitalization and Incidence of Hospitalization for All-cause LRTI, in UK Reconsented Participants

At the time of Second Year Analysis, incidences of RSV and all-cause LRTI hospitalization in UK reconsented participants only will be summarized by the treatment group. Descriptive statistics will be provided only.

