9.4.2 Primary Endpoint

The primary endpoint is the overall incidence of RSV LRTI hospitalization through the RSV season in healthy term and preterm infants in all 3 countries combined. The determination of RSV LRTI hospitalization is based on the criteria described in Section 8.1.2.2.

The efficacy of nirsevimab in preventing RSV LRTI hospitalization compared to no intervention will be estimated accounting for the follow-up time post-dosing/randomization up to the data cut-off date for the Primary Analysis as follows:

 $(1-(CN/NN)/(CC/NC)) \times 100\%$

where:

- CN and CC are the numbers of RSV LRTI hospitalization through the RSV season in the nirsevimab and the control (ie, no intervention) groups, respectively.
- NN and NC are the total person-time contributed by participants randomized in the nirsevimab and the control groups, respectively.

The 95% CI for the efficacy will be calculated by an exact method assuming a binomial distribution of the number of RSV LRTI hospitalizations in the nirsevimab group conditional on the total number in both groups accounting for the follow-up time post-dosing/randomization.

The superior efficacy of nirsevimab in preventing RSV LRTI hospitalization will be concluded if the lower bound of the efficacy is > 0%. The primary efficacy analysis of the primary endpoint will be performed on all randomized participants.

If a participant experiences multiple occurrences of the same primary endpoint, only the first episode will be considered. The following rules will be applied in the calculation of the total person-time for the follow-up time:

- The start date for the follow-up will be the date of randomization for participants who are randomized to no intervention and the date of dosing for participants who are randomized to nirsevimab.
- For the participants who do not have the primary endpoint at the time of the Primary Analysis, the end date for the efficacy follow-up will be the end of the RSV season, or the last available date with confirmation of no RSV LRTI hospitalization for the Primary Analysis whichever is earlier. The efficacy follow-up will be censored at the end date.
- For the participants who have the primary endpoint at the time of the Primary Analysis, the end date for the efficacy follow-up will be the date of hospital admission.

The above-described analysis on the primary endpoint will also be conducted on the PPAS.

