6.6.1. Primary Efficacy Analysis

The primary efficacy variable is defined as the overall incidence of RSV LRTI hospitalization through the RSV season in healthy term and preterm infants in all 3 countries combined, measured by $1 - \text{incidence rate ratio}$.

The null hypothesis of $(1 - (CN / NN) / (CC / NC)) \times 100\% \leq 0\%$ will be tested against the alternative hypothesis of $(1 - (CN / NN) / (CC / NC)) \times 100\% > 0\%$ at the $\alpha=0.05$ significance level.

where:

- CN and CC are the numbers of RSV LRTI hospitalization through the RSV season in the nirsevimab and the no intervention groups, respectively.
- NN and NC are the total person-time contributed by participants randomized in the nirsevimab and the no intervention groups, respectively.

If a participant experiences multiple occurrences of the same primary endpoint, only the first episode will be considered.

The following rules will be applied in the calculation of the total person-time for the follow-up time:

- The start date for the follow-up will be the date of randomization for participants who are randomized to no intervention, the date of treatment dosing for participants who are randomized to nirsevimab and treated, and the date of randomization for participants who are randomized to nirsevimab but not treated.
- For the participants who have the primary endpoint at the cut-off date for the Primary Analysis, the end date for the efficacy follow-up will be the date of hospital admission if the cut-off date is before the end of RSV season; otherwise the participants will be censored at the end of RSV season.
- For the participants who do not have the primary endpoint at the cut-off date for the Primary Analysis (see section 6.7.8), the efficacy follow-up will be censored at the end date defined in the following:
 - for the participants who continue in the study and had contact for safety events, the end date for the efficacy follow-up will be the end of RSV season, the last available date with confirmation of no RSV LRTI hospitalization or the cut-off date whichever is earlier.
 - for the participants who discontinued from the study before the end of RSV season and had contact for safety events, see Table 2 in section 3.1.4.

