6.6.2. Sensitivity Analyses for the Primary Objective

6.6.2.1. Analyses with Poisson Regression Model

A sensitivity analysis using a Poisson regression model with robust variance will be performed on All Randomized Set. The model will contain the following independent variables: the term of treatment group (ie, nirsevimab, no intervention), and age group at randomization (ie, $\text{age} \leq 3.0$ months, $\text{age} > 3.0$ to ≤ 6.0 months, $\text{age} > 6.0$ months), and country (ie, France, Germany and United Kingdom) as covariates, adjusting for the log of the follow-up time of the first event as an offset. No interaction terms will be included in the model. The efficacy of nirsevimab in preventing RSV LRTI hospitalization, defined as $(1 \text{ minus the incidence rate ratio}) \times 100\%$ and its corresponding 2-sided 95% CI will be estimated from the model by exponentiating the poisson model coefficients. Follow-up time for the log offset will be calculated as per Section 6.6.1. P-value will be provided.

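### The post-hoc all-events Poisson model for all-cause hospitalization keeps an offset that stops at the first admission, so repeat admissions are counted without their person-time

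*SAP*

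**What the plan says.** SAP 6.6.9 adds all-cause hospitalization as a post-hoc endpoint over five windows: through the RSV season, through 150 days, through 180 days, days 181 to 366, and through the end of 2022. The main post-hoc estimate uses the exact method on first episodes. Section 6.6.9.1.1 then adds a model: "The Poisson regression model described in section 6.6.2.1 is considered as a sensitivity analysis for the post-hoc analysis". The one modification it names is that "all hospitalizations are counted, not just the first episode". It also permits a negative binomial model if that fits better, particularly under overdispersion.

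Section 6.6.2.1 specifies the Poisson model as "adjusting for the log of the follow-up time of the first event as an offset", and adds: "Follow-up time for the log offset will be calculated as per Section 6.6.1". Section 6.6.1 was written for a first-event endpoint; for repeat events, "only the first episode will be considered". For an infant with the event, "the end date for the efficacy follow-up will be the date of hospital admission if the cut-off date is before the end of RSV season". When that condition is not met, a different rule takes over: "otherwise the participants will be censored at the end of RSV season". Protocol 9.4.2 has no such condition: "the end date for the efficacy follow-up will be the date of hospital admission".

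Section 6.6.9.1 carries the 6.6.1 follow-up rules over to the all-cause endpoint. Its added rules for the end-2022 window deal with infants without an event, early discontinuation, no contact, events after the window, and Beyfortus. None extends follow-up beyond a first admission.

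**The concern.** A rate model needs the events and the person-time to cover the same period. Counting the first episode and stopping the clock there is coherent. Counting every episode while still stopping the clock at the first is not, because later admissions are then divided by time in which they could not have occurred.

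The inflation grows with the admission rate, so it is larger in the arm with more admissions and does not cancel in the ratio. A sensitivity analysis should show whether the main estimate holds up. One that moves away from 1 by construction cannot do that cleanly.

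**Working it through.** **The plan's own figure.** There is none to reproduce. Neither document gives an all-cause hospitalization rate or a projected result for this analysis, so the rates below are assumptions.

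**Set-up.** Let *m* be the mean number of admissions per infant in the window (all admissions, not the proportion of infants admitted), with a constant hazard and window length 1. The expected time to first admission or window end is

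E(m) = (1 − e^(−m)) / m.

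With a treatment term only, the fitted rate in an arm is total events over total offset time. With full follow-up that is *m*; with the first-event offset it is *m*/E(m). Hence

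ratio as written = (m_N/m_C) × E(m_C)/E(m_N),

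where N is nirsevimab and C is no intervention.

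| m, C v N (assumed) | E(m), C v N | Rate inflation, C v N | Ratio, full follow-up | Ratio, first-event offset |
|---|---|---|---|---|
| 0.06 v 0.045 | 0.9706 v 0.9778 | 3.0% v 2.3% | 0.750 | 0.750 × 0.9706/0.9778 = 0.744 |
| 0.10 v 0.08 | 0.9516 v 0.9610 | 5.1% v 4.1% | 0.800 | 0.800 × 0.9516/0.9610 = 0.792 |

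Efficacy is therefore about 25.6% instead of 25.0%, and 20.8% instead of 20.0%.

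**Range.** The same formula over other control means:

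| Control mean m | True efficacy 20% becomes | True efficacy 40% becomes |
|---|---|---|
| 0.02 | 20.2% | 40.2% |
| 0.05 | 20.4% | 40.6% |
| 0.10 | 20.8% | 41.2% |
| 0.20 | 21.5% | 42.3% |

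With gamma frailty (shape 0.1 to 0.5), flat or front-loaded hazard, and m from 0.05 to 0.20, the shift is 0.3 to 2.7 percentage points. Simulated Poisson fits agree. With a true ratio of 0.8 and m = 0.06, the mean estimate is 0.791 with full follow-up and 0.786 with the first-event offset. With a true ratio of 0.6, m = 0.12 and frailty, it is 0.606 and 0.595.

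**Direction.** If m_N = m_C, then E(m_C)/E(m_N) = 1 and there is no bias. If m_N > m_C, the ratio is pushed further above 1.

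**Side effect on model choice.** In simulated data with no overdispersion (m = 0.06), Pearson chi-square over its degrees of freedom was 1.0 with full follow-up and 6.4 with the first-event offset, because infants admitted early get very short offsets. The offset alone could therefore prompt the switch to negative binomial.

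**The case against.** The strongest reply is textual. Section 6.6.1 ends a case's follow-up at admission only if the cut-off precedes the end of the season, and the close of 6.6.1 sets the season end to the cut-off date (28 February 2023). Taken literally, infants with an event are followed to season end, and the mismatch disappears in the through-season window. That stands as an ambiguity for that window. But this reading contradicts the first-event offset in 6.6.2.1 and the unconditional rule in protocol 9.4.2, and it does not address the 150-day, 180-day, day 181 to 366 or end-2022 windows.

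A second reply is that the offset wording belongs to a first-episode model and a programmer would extend it. Perhaps, but 6.6.9.1.1 names only the change in event count, and 6.6.9.1 retains the 6.6.1 rules. Going back to the Poisson model in protocol 9.4.2 does not help, because it also takes its follow-up time from the primary-endpoint rule.

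A third reply is that little depends on it. That is right: 6.6.9.1.1 bars p-values and any conclusion from this analysis on its own, and the main post-hoc estimate matches first episodes to first-event time.

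**Conclusion.** The concern holds, and it is minor. Followed as written, the all-events model counts repeat admissions without the time in which they arose, and the rate ratio moves away from 1. At the two assumed pairs of admission rates the shift is 0.6 to 0.8 percentage points of efficacy. Across the wider assumed range it runs from about 0.2 to 2.7 points.

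Three stronger readings are not supported:

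- A reader might infer that nirsevimab's benefit is always overstated. That requires a true ratio below 1. At 1 there is no bias, and above 1 an increase would be exaggerated.
- A reader might take the assumed rates as percentages of infants hospitalized. They are mean admissions per infant. If 6% v 4.5% of infants are admitted at least once, the correctly matched first-event rate ratio under a constant hazard is ln(0.955)/ln(0.94) = 0.744, so the gap between 0.744 and the risk ratio of 0.750 would not be bias.
- A reader might infer that the primary, key secondary or main post-hoc results are affected. They count first episodes only, so this mismatch does not arise there.

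**What to change.** Add to SAP 6.6.9.1.1 that when all hospitalizations are counted, the offset is the log of total follow-up in the window, up to the earliest of window end, the last date with known hospitalization status, or the Beyfortus date, whether or not an admission has occurred. State whether days in hospital count as time at risk, and that overdispersion is judged with this offset.

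Separately, reconcile the end-date clause for infants with an event in SAP 6.6.1 with 6.6.2.1 and protocol 9.4.2, so that the through-season window has one rule.

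The cost is a sentence or two of SAP text and a change to one derived variable. The dates required are already used elsewhere in the SAP, so no new data are needed.

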6.6.9.2.1. Algorithm for Follow-up Time

The start date for the follow-up will be the date of randomization for participants who are randomized to no intervention, the date of treatment dosing for participants who are randomized to nirsevimab and treated, and the date of randomization for participants who are randomized to nirsevimab but not treated.

For the participants who have the event of interest in the corresponding timeframe for the Second Year Analysis, the end date of the follow-up time will be the date of hospital admission; otherwise the participants will be censored as defined in the following:

- **From 366 Days Post-Dosing/Randomization to 511 Days Post-Dosing/Randomization**

The analysis will be performed only in participants without the studied event before Day 366.

For UK reconsented participants who completed the study, the end date of the follow-up time will be Day 511 or last available date with confirmation of no RSV/all-cause LRTI hospitalizations, whichever is earlier.

For UK reconsented participants who had contact for safety events after reconsented and discontinued from the study before Day 511, the end date of the follow-up time will be the last available date with confirmation of no RSV/all-cause LRTI hospitalizations.

For UK reconsented participants who had no contact for safety events at all after reconsenting, the end date of the follow-up time will be the reconsent date.

Notes:

- If the event of interest occurs after Day 511, it will not be considered and then the end date will be Day 511.
- If a participant receives Beyfortus as part of a routine immunization, any event occurring after Beyfortus immunization but between Day 366 and Day 511 will not be considered and the end date will be the date of injection of Beyfortus.

- **From 512 Days Post-Dosing/Randomization to 731 Days Post-Dosing/Randomization**

The analysis will be performed only in participants without the studied event before Day 512.

For UK reconsented participants who completed the study, the end date of the follow-up time will be Day 731 or last available date with confirmation of no RSV/all-cause LRTI hospitalizations, whichever is earlier.

For UK reconsented participants who had contact for safety events after reconsented and discontinued from the study, the end date of the follow-up time will be the last available date with confirmation of no RSV/all-cause LRTI hospitalizations.

For UK reconsented participants who had no contact for safety events at all after reconsenting, the end date of the follow-up time will be the reconsent date.

Notes:

- If the event of interest occurs after Day 731, it will not be considered and then the end date will be Day 731.
- If a participant receives Beyfortus as part of a routine immunization, any event occurring after Beyfortus immunization but between Day 512 and Day 731 will not be considered and the end date will be the date of injection of Beyfortus.

- **Through 511 Days Post-Dosing/Randomization**

For UK reconsented participants who completed the study, the end date of the follow-up time will be Day 511 or last available date with confirmation of no RSV/all-cause LRTI hospitalizations, whichever is earlier.

For UK reconsented participants who had contact for safety events after reconsented and discontinued from the study before Day 511, the end date of the follow-up time will be the last available date with confirmation of no RSV/all-cause LRTI hospitalizations.

For UK reconsented participants who had no contact for safety events at all at Day 511, the end date of the follow-up time will be the start date.

Notes:

- If the event of interest occurs after Day 511, it will not be considered and then the end date will be Day 511.
- If a participant receives Beyfortus as part of a routine immunization, any event occurring after Beyfortus immunization but before Day 511 will not be considered and the end date will be the date of injection of Beyfortus.

- **Through 731 Days Post-Dosing/Randomization**

For UK reconsented participants who completed the study, the end date of the follow-up time will be Day 731 or last available date with confirmation of no RSV/all-cause LRTI hospitalizations, whichever is earlier.

For UK reconsented participants who had contact for safety events after reconsented and discontinued from the study, the end date of the follow-up time will be the last available date with confirmation of no RSV/all-cause LRTI hospitalizations.

For UK reconsented participants who had no contact for safety events at all at Day 731, the end date of the follow-up time will be the start date.

Notes:

- If the event of interest occurs after Day 731, it will not be considered and then the end date will be Day 731.
- If a participant receives Beyfortus as part of a routine immunization, any event occurring after Beyfortus immunization but before Day 731 will not be considered and the end date will be the date of injection of Beyfortus.

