 - for the participants who had no contact for safety events at all throughout the efficacy follow-up period, the end date for the efficacy follow-up will be date of randomization for participants who are randomized to no intervention, the date of treatment dosing for participants who are randomized to nirsevimab and treated, and the date of randomization for participants who are randomized to nirsevimab but not treated.

The total person-time for the follow-up time of each participant will be calculated as:

Person-months = (the end date - the start date + 1)/30.4375.

NN (days), the total person-time contributed by participants randomized in the nirsevimab, will be the sum of person-months for all the participants in the nirsevimab group. And NC (days), the total person-time contributed by participants randomized in the no intervention group, will be the sum of person-months for all the participants in the no intervention group.

The 2-sided 95% CI for the efficacy will be calculated by an exact method assuming a binomial distribution of the number of RSV LRTI hospitalizations in the nirsevimab group conditional on the total number in both groups (described by Breslow and Day⁷) accounting for the follow-up time post-dosing/randomization.

The superior efficacy of nirsevimab in preventing RSV LRTI hospitalization is concluded if the lower bound of 2-sided 95% CI of the efficacy is $> 0\%$. P-value will also be provided. The primary efficacy analysis of the primary endpoint will be performed with the All Randomized Set.

RSV season is the period of increased RSV infection. For the purpose of efficacy analyses, the start of the RSV season will be defined on a country-by-country basis and will be based on country-specific epidemiological surveillance and the cut-off date (28Feb2023, except for site parent contact and medical call center contact, for which the date of database lock for Primary Analysis will be used) will be used as end dates.

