6.6.7.8. Follow-up

Number and percentage of participants will be provided for:

- Monthly responses in eDiary according to the analysis window in Section 5.1.4.

In addition, at the time of First Year Analysis, follow-up time in months will be described for all participants (based on the primary endpoint RSV LRTI Hospitalizations), participants with RSV LRTI Hospitalizations, participants with Very Severe RSV LRTI, participants with Hospitalizations for all-cause LRTI at the following timeframes (see Section 6.1 for details on the descriptive statistics):

- Through the RSV Season (overall and in each country)
- Through Day 151 post-dosing/randomization (overall and in each country)
- Through Day 181 post-dosing/randomization (overall and in each country)
- From 181 days post-dosing/randomization to 366 days post-dosing/randomization in participants with no event before Day 181 (overall and in each country, excluding participants with very severe RSV LRTI)

Follow-up time in months will also be summarized at the time of Second Year analysis:

- From 366 days post-dosing/randomization to 731 days post-dosing/randomization in UK reconsented participants. However, this will not be summarized for subgroup of participants with Very Severe RSV LRTI.
- From 366 days post-dosing/randomization to 511 days post-dosing/randomization in UK reconsented participants. However, this will not be summarized for subgroup of participants with Very Severe RSV LRTI.
- From 512 days post-dosing/randomization to 731 days post-dosing/randomization in UK reconsented participants. However, this will not be summarized for subgroup of participants with Very Severe RSV LRTI.
- Through Day 511 post-dosing/randomization in UK reconsented participants. However, this will not be summarized for subgroup of participants with Very Severe RSV LRTI.
- Through Day 731 post-dosing/randomization in UK reconsented participants. However, this will not be summarized for subgroup of participants with Very Severe RSV LRTI.
- Through Day 366 post-dosing/randomization in UK reconsented participants (recurrent wheeze event)
- From Day 366 post-dosing/randomization to Day 731 post-dosing/randomization in UK reconsented participants (recurrent wheeze event)
- Through Day 731 post-dosing/randomization in UK reconsented participants (recurrent wheeze event)

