6.6.9. Post-hoc Analyses

In the context of the VAS00006 study (for which the objectives of interest stated in the study protocol are to assess the efficacy of nirsevimab in preventing RSV LRTI hospitalization, very severe RSV LRTI, all-cause LRTI compared to no intervention), there is a need to conduct a post-hoc analysis, for a less specific outcome in order to assess the risk reduction in all-cause hospitalizations associated with nirsevimab and describe in specific timepoints, the incidence of RSV LRTI hospitalization and all-cause LRTI hospitalization in UK reconsented participants during the study.

Additional objectives for the post-hoc analysis:

- To assess the relative risk reduction (i.e., efficacy) in all-cause hospitalizations associated with nirsevimab compared to no intervention.
- To describe in each treatment group the incidence of RSV LRTI hospitalization and all-cause LRTI hospitalization in UK reconsented participants during the study.

Additional endpoints for the post-hoc analysis:

- Incidence of all-cause hospitalization, overall and in each country
 - Through the RSV season, through 150 days post-dosing/randomization, through 180 days post-dosing/randomization, from 181 days post-dosing/randomization to 366 days post-dosing/randomization,
 - Through the end of year 2022.
- Incidence of RSV LRTI hospitalization, in UK reconsented participants
 - From 366 days post-dosing/randomization to 511 days post-dosing/randomization, from 512 days post-dosing/randomization to 731 days post-dosing/randomization, through 511 days post-dosing/randomization, through 731 days post-dosing/randomization.
- Incidence of all-cause LRTI hospitalization, in UK reconsented participants
 - From 366 days post-dosing/randomization to 511 days post-dosing/randomization, from 512 days post-dosing/randomization to 731 days post-dosing/randomization, through 511 days post-dosing/randomization, through 731 days post-dosing/randomization.

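### SAP 6.6.9.2.1 starts the clock at Day 1 for the Day 366–511 and Day 512–731 windows, so the follow-up months planned for them include time before the window opens

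*SAP*

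**What the plan says.** SAP 6.6.9.2.1 opens with a start rule placed above all four UK windows: "The start date for the follow-up will be the date of randomization for participants who are randomized to no intervention". Treated nirsevimab children start at dosing, and untreated ones at randomization. The four windows follow: Days 366–511, Days 512–731, through Day 511 and through Day 731.

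The first two windows change the risk set and the end date. For Days 512–731, "The analysis will be performed only in participants without the studied event before Day 512"; Days 366–511 has the matching restriction at Day 366. Events after the window end are ignored. Neither window resets the start date.

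In these two windows, for children "who had no contact for safety events at all after reconsenting, the end date of the follow-up time will be the reconsent date". Receipt of Beyfortus also ends follow-up, at the injection date.

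The only person-month formula in the SAP is in 6.6.1: "Person-months = (the end date - the start date + 1)/30.4375".

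SAP 6.6.7.8 plans follow-up time in months at the Second Year Analysis, with separate rows for each window, among them "From 366 days post-dosing/randomization to 511 days post-dosing/randomization in UK reconsented participants" and "Through Day 511 post-dosing/randomization in UK reconsented participants". The opening of 6.6.9 says that "there is a need to conduct a post-hoc analysis". For the UK LRTI windows, 6.6.9.2 adds: "Descriptive statistics will be provided only".

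**The concern.** A window that opens at Day 366 or Day 512 and admits only children event-free up to then should count time from its opening day. Under the rule as written, each child brings in a long stretch in which no counted event can occur. The follow-up rows in 6.6.7.8 would then not report what their labels say.

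Protocol 4.2 says the extension is meant to address second-season antibody-dependent enhancement. How long children were actually observed in each part of the second year is basic context for reading those results. Follow-up counted from Day 1 hides incomplete observation: a child last confirmed event-free soon after the window opens looks nearly as well followed as one seen to its end.

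**Working it through.** **Inputs**
- Start: Day 1, randomization or dosing (SAP 6.6.9.2.1).
- Window ends: Day 511 and Day 731 (SAP 6.6.9.2.1).
- Day numbering: Day 1 is randomization or immunization, with no Day 0 (SAP 5.1.1). This agrees with the protocol schedule, where D366 is V01 + 365 days and D731 is V01 + 730 days.
- Months = (end − start + 1)/30.4375 (SAP 6.6.1; applying it to 6.6.9.2.1 is an inference).

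The documents state no follow-up length for these windows, so there is no planned figure to reproduce.

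**Fully followed, event-free child**

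| Window | As written | Clock from window opening | Excess | Ratio |
|---|---|---|---|---|
| Days 366–511 | 511 − 1 + 1 = 511 days (16.79 months) | 511 − 366 + 1 = 146 days (4.80 months) | 365 days (11.99 months) | 511/146 = 3.50 |
| Days 512–731 | 731 − 1 + 1 = 731 days (24.02 months) | 731 − 512 + 1 = 220 days (7.23 months) | 511 days (16.79 months) | 731/220 = 3.32 |

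The as-written values equal those of the through-Day-511 and through-Day-731 rows, so for such a child the two rows of each pair cannot be told apart.

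**Any end date inside the window**

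For a window opening on day X and an end date e within it, the excess is e − (e − X + 1) = X − 1. That is 365 days for X = 366 and 511 days for X = 512.
- Event on Day 440: 440 days as written, 440 − 366 + 1 = 75 in the window; excess 365.
- Event on Day 620: 620 days as written, 620 − 512 + 1 = 109 in the window; excess 511.
- Last confirmation on Day 370: 370 days as written, 370 − 366 + 1 = 5 in the window. The child shows 370/511 = 72% of the full as-written value but has 5/146 = 3% of the window.

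**End date outside the window** (illustrative dates)

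The constant excess does not apply here. The protocol's schedule of activities lets the consent addendum be obtained before the D366 call or as late as D731.
- Reconsent on Day 350, no later contact: 350 days (11.5 months) in both windows; time in either window is 0.
- Beyfortus on Day 400: 400 days in the Day 512–731 window; time in that window is 0.
- Reconsent on Day 600, no later contact: 600 days in a window that is 146 days long.

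The documents do not say how many children fall in these groups.

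**The case against.** The strongest reply is that 6.6.7.8 does not cite 6.6.9.2.1, its rows are labelled by window, and the formula sits in 6.6.1. A programmer could take the labels at face value and count only time in the window. That part stands: the link is the likely reading, not a stated one. But 6.6.9.2.1 is the only algorithm the SAP gives for follow-up time in these two windows, and no start date specific to them appears in it or in 6.6.7.8. A programmer who counts window time departs from the written rule, so the sentence is still needed.

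The second reply is that little depends on it. This also stands. The windows are post-hoc and descriptive, the SAP names no person-time rate or arm ratio in them, and version 6.0 removed inference for the UK reconsented endpoints.

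A reader might infer that the rule biases the comparison between arms. The documents do not support that: both arms start at Day 1, and no between-arm estimate is planned in these windows. A reader might also extend the point to Days 181–366, to the Day 366–731 analysis in 6.6.4.3.6, or to a conflict with the second-year period in 5.1.3. Neither of those analyses states a randomization start for its window. The 5.1.3 period is a Treatment Period, used to classify adverse events, and 6.6.9.2.1 does not refer to it. Those are at most matters of wording.

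**Conclusion.** The rule is wrong as written for two of its four windows, and the effect is minor. For every child whose follow-up ends inside the window, the excess is exactly 365 days (Days 366–511) or 511 days (Days 512–731). It is not a constant for all children, because those who end before or after the window carry a different amount. The smallest overstatement among children ending inside the window is at the window end, 3.50 and 3.32 times, since e/(e − X + 1) falls as e rises.

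The output affected is the follow-up-month description for these two windows in 6.6.7.8. Counts and percentages of children with events do not change, and neither do the primary and key secondary analyses. It would go too far to say that second-year incidence will be understated about threefold: that would follow only if someone later built a person-month rate on this time, and it would then apply to both arms by about the same factor.

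The conclusion rests on two readings: that the 6.6.1 formula applies to 6.6.9.2.1, and that the rows in 6.6.7.8 use the 6.6.9.2.1 algorithm.

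**What to change.** In 6.6.9.2.1, keep the Day 1 start for the through-Day-511 and through-Day-731 windows. For the other two:
- Start the clock at Day 366 (Days 366–511) or Day 512 (Days 512–731).
- Keep the event-free restriction, and cap end dates at the window end.
- Give zero window time to a child whose end date, for whatever reason, precedes the window.
- For a child with no contact after reconsenting, count no time beyond the last date with confirmation of no event. Capping alone is not enough: a Day 600 reconsent date capped at Day 511 would credit all 146 days to a child with no later contact.

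Add a cross-reference to 6.6.9.2.1 in the two matching rows of 6.6.7.8.

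The cost is a few sentences in the SAP and a change to one derivation. It needs no new data and changes no percentage or confirmatory result.
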